6.3 Treatment

- If criteria are met, patients will be randomized by the study coordinator, per methods determined by the statistician. The randomization allocation will be shared with the surgical team from the study coordinator to the surgeon prior to the surgery.
 - If randomized to the botulinum arm, patients will undergo the standard minimally invasive esophagectomy performed at RPCI, including botulinum injection. The intraoperative procedure for botulinum toxin injection is as follows: 100 units of botulinum toxin is dissolved in 10 mL normal saline. After preparation of the gastric conduit, including mobilization and transection, the 10 mL of botulinum toxin solution is injected with a thoracoscopic needle intramuscularly at the anterior pyloric ring, in 2-3 separate areas.

- If randomized to the no botulinum arm, patients will undergo the standard minimally invasive esophagectomy performed at RPCI **excluding** the pyloric drainage procedure with botulinum injection.
- Standard Post Anesthesia Care Unit (PACU) protocols for patient recovery from surgery. Patients will be continuously monitored both intraoperatively and during the recovery period.
- Clinical Events of Interest and Adverse Events will be recorded throughout the time of entry into the operating room until the post-operative follow-up. Refer to **Section 7.1.3** for method of recording clinical events of interest and adverse events.

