4 METHODOLOGY

4.1 Study Design

This is a double arm, single-blinded randomized trial evaluating the use of botulinum toxin injection as a pyloric drainage procedure. The study is expected to accrue patients over 4 years. The study schema is depicted below in **Figure 1**.

Figure 1 Study Schema

All patients considered for minimally invasive esophagectomy in our surgery practice will receive routine work-up and multidisciplinary evaluation and care for esophageal carcinoma, which may include neoadjuvant therapy. Patients will be given a patient consent form that will inform them of the possible risks and benefits of this study. Patients will undergo the standard of care preoperative work-up, during which it will be determined if they meet the inclusion and exclusion criteria summarized in **Section 5.1** and **Section 5.2** prior to enrollment in the study. If criteria are met, patients will be randomized by the study coordinator, per methods determined by the statistician. The randomization allocation will be shared with the surgical team from the study coordinator to the surgeon prior to the surgery and discussed during the surgical time-out. The next 50 patients who meet the study criteria will be randomized to either the intrapyloric botulinum injection arm or the non-botulinum treatment arm. All participants will sign a surgical consent prior to minimally invasive esophagectomy.

All patients will undergo routine minimally invasive esophagectomy. If randomized to the botulinum arm, patients will undergo the standard minimally invasive esophagectomy performed at RPCI, including intra-pyloric botulinum injection. If randomized to the no botulinum arm, patients will undergo the standard minimally invasive esophagectomy performed at RPCI **excluding** the pyloric drainage procedure with botulinum injection. The patient and radiologist

will be blinded to the treatment arm. The surgeon, due to the nature of the intervention, will not be blinded to the treatment arm.

The standard of care for minimally invasive esophagectomy at RPCI is outlined in the following postoperative pathway. **All patients follow this pathway unless clinical status dictates otherwise:**

- Patients leave the operating room with a nasogastric tube (NGT) tip at or beneath the esophago-gastric anastomosis, and a feeding jejunal-tube (j-tube).

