4.2 Target Accrual and Study Duration

A maximum of 50 evaluable patients at RPCI will be enrolled. Accrual is expected to take up to 6 years.

This target accrual and study duration is highly feasible based off the high volume of patients with esophageal carcinoma undergoing minimally invasive esophagectomy at RPCI. An interim analysis will occur after 30 patients have been enrolled.

Study participants will be followed for data collection for 90 days (routine post-esophagectomy follow-up care and surveillance, per standard of care).

A patient will be replaced on study if the following deviations from the original surgical plan occur:

- the surgical procedure is converted to open technique or,
- a cervical anastomosis is performed or,
- a patient does not complete the postoperative evaluation through the nuclear medicine emptying study obtained within \pm 14 days of post-operative visit #2.

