9.2 Randomization

Patients will be randomized in a 1:1 fashion to the Botox and non-Botox treatment arms using a permuted block design. Participants will be stratified on the receipt of neoadjuvant chemoradiotherapy, smoking status, and diabetes. Participants will be randomized prior to the

minimally invasive esophagectomy, after signing consent for the surgical procedure. The randomization list will be developed by the Department of Biostatistics and Bioinformatics and provided to the study coordinator, who will then relay the information to the surgical team at the start of the procedure.

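### The unblinded surgeon learns the arm before the intraoperative events that lead to replacement, although the arm is needed only at the injection step, so replacement can depend on arm

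*Combined protocol and SAP*

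**What the plan says.** **When the arm is disclosed.** Section 4.1 has the coordinator tell the surgeon "prior to the surgery and discussed during the surgical time-out". Section 6.3 also says before surgery: "from the study coordinator to the surgeon prior to the surgery". Section 9.2 has the coordinator "relay the information to the surgical team at the start of the procedure", and places randomisation itself before the esophagectomy, after surgical consent.

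**Who is blinded.** The patient and the radiologist are. For the operator, section 4.1 says: "The surgeon, due to the nature of the intervention, will not be blinded to the treatment arm".

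**What leads to replacement.** Section 4.2 replaces a patient if "the surgical procedure is converted to open technique or" if a cervical anastomosis is performed. A third trigger, not completing evaluation through the nuclear medicine study, arises after surgery and is outside this point. The same section sets the target as 50 evaluable patients.

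**When the arm is needed.** Section 6.3 places the injection "After preparation of the gastric conduit, including mobilization and transection".

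**How the primary outcome is analysed.** Section 9.4 states the intent-to-treat principle and a one-sided CMH test. No section says that replacement is decided or reviewed without knowledge of the arm, or how replaced patients are followed and analysed.

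**The concern.** Open conversion and the choice of anastomosis are the operating surgeon's decisions. Under the plan they are taken by someone who already knows the arm, and they determine whether the patient is replaced. If a replaced patient does not count among the 50, the analysed set is partly shaped after randomisation by a person aware of the allocation, and the comparison loses the protection that randomisation gives.

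This needs no bad faith. A slightly different threshold for a difficult case in one arm would be enough. Expectations are not neutral either: sections 1.1 and 1.2 state the investigators' hypothesis that the injection does not work. Any bias could therefore run in either direction.

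The early disclosure also appears unnecessary, because the operation is the same in both arms until the injection step.

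**Working it through.** **1. Order of events, set side by side**

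| Step | Source | Arm known to surgeon? |
|---|---|---|
| Randomisation before the operation | 9.2 | Not yet, or being passed on |
| Disclosure before surgery and at the time-out, or at the start of the procedure | 4.1, 6.3; 9.2 | Yes from here |
| Conduit prepared (mobilised and transected) | 6.3 | Yes |
| Injection, if allocated | 6.3 | Yes; first step that needs it |
| Conduit moved into the chest and joined | order inferred from 1.1 | Yes |

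Open conversion can occur at any point in the operation. The anastomosis comes after the conduit is formed. Both triggers therefore follow disclosure on either timing. The gap between 4.1/6.3 and 9.2 is minor and does not change this.

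**2. Reproducing the plan's own figures (section 9.1)**

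Inputs: 15 per arm at the interim and 25 per arm at the end; interim boundary 0.011396; stop if the odds ratio exceeds 1; final boundary 0.046533; rates 0.30 v 0.70. The design was enumerated exactly, without strata.

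- Power: 86.1% with the exact test, 86.0% with continuity correction and 91.6% with uncorrected CMH. An eight-stratum CMH simulation, with assumed stratum shares and blocks, gives about 88%. Stated: 85.0%.
- Early stopping for inferiority when both rates are 0.70: 42.1%. Stated: 42.1%.
- Type I error: 2.5% exact, 5.3% uncorrected CMH, 4.6–5.3% eight-stratum CMH. Stated: 4.3%.

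No single variant matches every stated figure, so two tests are carried forward.

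**3. How much arm-dependent replacement could matter (assumption)**

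Let both true rates be 0.70. Suppose a share r of would-be delayed botulinum patients, and the same share of would-be non-delayed controls, are replaced. The analysed rates become

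- botulinum: 0.70(1−r) / [0.70(1−r) + 0.30]
- control: 0.70 / [0.70 + 0.30(1−r)]

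At r = 0.10 these are 0.63/0.93 = 0.677 and 0.70/0.97 = 0.722. The share of patients replaced is 0.70 × 0.10 = 7% of botulinum and 0.30 × 0.10 = 3% of control.

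| r | False positive, uncorrected CMH | False positive, exact test |
|---|---|---|
| 0 | 5.3% | 2.5% |
| 0.05 | 7.4% | 3.6% |
| 0.10 | 10.1% | 5.2% |
| 0.20 | 18.3% | 10.6% |

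This is pessimistic: it assumes that replacement tracks an outcome not yet observed, and that it favours botulinum in both arms.

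**4. Leverage of one patient**

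One patient is 1/25 = 4% of an arm. With x delayed on botulinum, m delayed in total, n = 25 and N = 50, z = (x − nm/N)/√V, where V = n²m(N−m)/[N²(N−1)].

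- 10 v 16: (10 − 13)/√3.184 = −1.681, one-sided p = 0.0463, inside 0.046533.
- 11 v 16: (11 − 13.5)/√3.168 = −1.404, p = 0.080, outside.

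The crossing depends on the test. For 10 v 16 the continuity-corrected p is 0.081 and the exact p is 0.078, so neither was significant to begin with.

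**5. How many patients could be exposed**

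The documents give no rate of conversion or cervical anastomosis. If it were 5–10% (assumption), 0.05 × 50 = 2.5 to 0.10 × 50 = 5 patients would be affected.

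**The case against.** The strongest reply is that disclosure timing matters only because of the replacement rule. If every randomised patient is analysed, as section 9.4 implies, an arm-aware conversion cannot select the analysed set, so the repair belongs in the analysis set. That largely stands, and it is why the fix below has two parts. It does not make early disclosure harmless: section 4.2 as written replaces these patients, and knowing the arm can still influence operative decisions for no benefit before the injection.

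A second reply is that the surgeon cannot know the outcome when converting. It is a scan around Postoperative Visit #2, read by a blinded radiologist. This is fair. It limits the likely size of any bias and is why the table above is a pessimistic case.

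Four stronger readings are tempting, and the documents do not support them:

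- *That the surgeon will select patients by arm.* The text shows an opportunity, not that it would be used.
- *That section 4.2 removes patients from the analysis.* It says they are replaced. Removal is an inference from that word and the evaluable-patient target, and it conflicts with section 9.4.
- *That releasing the arm later closes the route, and that patients converted earlier would then never be randomised.* Section 9.2 randomises before the operation, so later release alone leaves early converts randomised. Conversion or a cervical anastomosis can also follow the injection.
- *That 4.1/6.3 and 9.2 seriously contradict each other.* They can be read as successive steps of one process, with the surgeon told first and the team at the time-out.

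**Conclusion.** The point holds as an avoidable opportunity for arm-aware replacement. Under all three sections the unblinded surgeon has the allocation before the events that trigger replacement, and section 6.3 does not need it until the conduit is prepared. Together with the target of 50 evaluable patients, this conflicts with the stated intent-to-treat principle.

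The size of any bias cannot be determined from the documents. The illustrated doubling of the false-positive rate at r = 0.10 rests on equal true rates of 0.70, outcome-related replacement favouring botulinum, and an unstratified analysis that omits replaced patients. The one-patient example holds only for the uncorrected, unstratified test. Moving the disclosure narrows the route to bias; only analysing all randomised patients removes its effect on who is analysed.

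**What to change.** 1. In sections 4.1, 6.3 and 9.2, use one rule: randomisation and release of the allocation both take place immediately before the injection step, after the conduit is prepared and once the surgeon has recorded that the minimally invasive approach and the planned intrathoracic anastomosis still stand.
2. Amend the sentence in 9.2 that randomises before the esophagectomy, and take disclosure of the arm out of the pre-incision time-out in 4.1. Only with this change are patients converted earlier never randomised.
3. Because a deviation can still occur afterwards, reconcile 4.2 with 9.4: keep every randomised patient in the intent-to-treat primary analysis, state how a missing scan is handled, and report conversions and cervical anastomoses by arm with reasons.

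**Cost.** Protocol wording, and a call or database release during the operation. The stratification factors (neoadjuvant chemoradiotherapy, smoking, diabetes) are recorded at baseline, so the list can be used at that moment. The downsides are a short wait, having the drug available in theatre whichever arm is drawn, and a team confirmation of the arm at the point of release instead of at the time-out. Injection technique, eligibility and the target number are unchanged.

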6.4 Inpatient Postoperative Follow-Up Evaluations

The following evaluations will be performed during the **inpatient postoperative course (surgery to discharge), unless otherwise clinically indicated.**:

Patients will follow Roswell Park standard of care postoperative pathway for minimally invasive esophagectomy (refer to Section 4.1), unless otherwise clinically indicated. This includes:

- Initial postoperative care in the intensive care unit or intermediate care unit, based on clinical status, with nursing care and vital signs per hospital unit standard:
- At the minimum daily physical examination (including vital signs).
- Laboratory analysis, including hematology (CBC with automated differentials) and chemistry (CMP), at least on a daily basis until Postoperative Day 6.
- Standard inpatient postoperative evaluations after minimally invasive esophagectomy include daily chest x-ray for at least four days postoperatively, and occasionally a CT scan of the chest if clinically indicated.
- Gastrograffin swallow study/CT esophagram is obtained to evaluate for any signs of anastomotic leak.
- Clinical evaluation of symptoms will be evaluated by the participant's care team, including inpatient nurses, mid-level providers, surgical fellows, operating surgeon, speech therapist, occupational or physical therapists, dieticians, and documented in the RPCI electronic medical record (EMR).
- Speech therapy evaluation for any dysphagia or signs of aspiration.
- Nutritional assessments will be performed by a dietitian familiar with the study. The initial evaluation will be performed in the outpatient setting if there are signs of malnutrition or inability to tolerate oral intake at the preoperative visit. Otherwise the standard is to perform the initial nutritional assessment in the immediate postoperative period. Patients will be monitored by the dietitian Monday-Friday while an inpatient, and then at each subsequent follow-up office visit, and assessment documented in the RPCI EMR.
- Nutritional goals are as follows: By hospital discharge, patients are expected to meet 50% of their total nutritional requirements orally and 50% by supplemental j-tube feeds. On

Postoperative Day #6, \pm 1 day, patients will undergo a 24-hour calorie count, to objectively assess oral intake. By Postoperative Day #21, patients should meet 75% nutritional requirements orally and 25% j-tube feeds, and by postoperative week #5, 100% oral calories. The postoperative day that each of these goals are met will be recorded (Day tolerating 50% oral feeds, 75% oral feeds, 100% oral feeds).

- Concomitant medication: List any ongoing medications with dose changes, as applicable. Patients may take opiates in the postoperative period, including on the day of the gastrografin swallow study/CT esophagram, and type and dosage will be recorded.
- Clinical Events of Interest and Adverse Events

Patients will be discharged from the hospital if they are medically stable and tolerating 100% of nutritional needs with a combination of orally and supplemental through j-tube:

- Any clinical signs of delayed gastric emptying causing regurgitation, vomiting, or aspiration will delay hospital discharge until the risk of aspiration is low.
- Hospital length of stay attributed to delayed gastric emptying: If patients have intractable nausea and vomiting, or experience a pulmonary event related to aspiration, this will be recorded as attributed to delayed gastric emptying.

6.5 Criteria for Retreatment

- Patients with “severe” delayed gastric emptying assessed radiographically or clinically at any time will be considered for endoscopic procedures for gastric outlet obstruction, including pyloric botulinum toxin injection or balloon dilation, or operative procedure. This is irrespective of whether a patient was initially treated with botulinum toxin at the minimally invasive esophagectomy; patients randomized to the botulinum toxin group may undergo additional botulinum toxin injection endoscopically. The maximum dose of botulinum toxin a patient may receive for this study in the three-month period is 300 units. Each of these procedures- when a patient undergoes a therapeutic endoscopic procedure or returns to the operating room- will be defined as a secondary procedure.
- Development of “severe” delayed gastric emptying as assessed by nuclear medicine study will be considered a failure of the experimental procedure and will be included in the primary analysis. Requirement for secondary procedure or development of “severe” delayed gastric emptying as assessed by parameters other than the nuclear medicine study will be included in the secondary analysis.
- Patients with “moderate” delayed gastric emptying assessed radiographically or clinically at any time will be considered for initiation of promotility agents. Development of “moderate” delayed gastric emptying will be included in the secondary analysis.

6.6 Outpatient Postoperative Follow-Up Visits

Study participants will be followed for data collection for 90 days (routine post-esophagectomy follow-up and surveillance, per standard of care). The following evaluations will be performed during the outpatient postoperative course, unless otherwise clinically indicated:

- In the postoperative period, patients return to office for outpatient follow-up approximately one to three weeks after discharge (“Postoperative Visit #1”). This visit is standard of care and can be scheduled per PI discretion. Physical exam and vital signs will be conducted at this visit. The dietician will assess oral intake, and supplemental tube feeds adjusted accordingly. Day until patient tolerates 75% and 100% of nutritional needs orally will be recorded as per nutritionist assessment.
- As a participant in this study, patients in both randomization groups will undergo a nuclear medicine emptying study. The nuclear medicine emptying study may occur within the window of Postoperative Visit #2 (\pm 14 days) to assess dynamic conduit function. This test can be extended beyond post-operative Visit #2 at PI’s discretion. Patients will be monitored for any symptoms of delayed gastric emptying during this time by questionnaire (See **Appendix C**), to determine if nuclear medicine study findings correlate with concurrent clinical symptoms.
 - Prior to the nuclear medicine emptying study, the patient must be fasting for at least 6 hours, including oral intake and any supplemental j-tube feeds. If the patient is a diabetic, the glucose level should be measured and less than 275 mg/dL within 2 hours of the study. Opiates must be held for 48 hours prior to the study. Patients should not be on any of the medications listed in **Appendix B** within the 48 hours prior to the study. Patients will remain in the nuclear medicine suite during this time, and will be required to sit upright, and may walk around the room. During the study, for the time between the images, the patients may be sitting, standing, or walking, but should remain in close proximity to the nuclear medicine facility.
- Post-surgical symptom evaluation based on clinical factors during the outpatient follow-up visits, and additionally by phone conversation between outpatient follow-up appointments if clinically indicated.
- At Postoperative Visit #2, patients will be assessed for quality of life as measured by EORQLQ-C30 OES18 questionnaire (**Appendix D**). This will usually occur in the office around postoperative week six to eight. However, if the patient remains hospitalized during this time point, the questionnaire will be administered once between Postoperative Days 35-42.
- Concomitant medications: List any ongoing medications with dose changes, as applicable.
- Clinical Events of Interest and Adverse Events

Participants who are unavailable for follow-up evaluations should be classified as lost to follow-up for one of the following reasons:

- Lost to follow-up: For a participant to be considered lost to follow-up, the investigator must make two separate attempts to re-establish contact with the participant. The attempts to re-establish participant contact must be documented (e.g., certified letter).

- Death: Date and cause of death will be recorded for those participants who die within 30 days of surgery (telephone verification is acceptable).

